2.2.5 Pharmacokinetic endpoints

Pharmacokinetic endpoint analysis will be described in a separate SAP.

2.3 Overall Trial Design

This trial is a prospective, multicenter, open-label, non-controlled trial in female subjects, age 15 or above who present to the clinic seeking contraception, who are postmenarcheal and premenopausal. Breastfeeding women are allowed to participate in the trial.

At V1a (screening), informed consent/assent will be obtained and the screening procedures will be performed. At V1b, after the results of the laboratory tests have confirmed the subject's eligibility, the subject will be provided with the investigational medicinal product (IMP) and an electronic diary and the subject will be instructed in their use. On anticipated start date of Cycle 1+2 days, the trial staff will call the subject for the confirmation of IMP start date. Afterwards, the subjects will attend Visits 2 to 5 at Day 20±2 of the 1st, 3rd, 6th and 9th cycle and Visit 6 at Day 29±2 of the 13th cycle. The follow-up (Visit 7) will take place 10-14 days after Visit 6. Once a month, on Day 10 (+ 2 days) of each cycle, the subjects will be contacted by the site staff to collect information on any adverse events which might have occurred.

The trial will include women who have never used hormonal contraceptives before consent/assent (naïve users), women who have not used hormonal contraceptives in the past three months before consent/assent or who have used hormonal contraceptives in the past but have a contraceptive-free time of less than three months before consent/assent (previous users) as well as women directly switching from another hormonal method (switchers). Women who have used hormonal contraceptives in the past but have a contraceptive-free time of less than three months before consent/assent are allowed to be included into the trial if they had at least one complete menstrual cycle before enrollment.

For naïve users and previous users, the first IMP intake will be on the first day of the next menstrual bleeding after Visit V1b. (If the menstrual bleeding starts in the evening, and the subject prefers to take her pill in the morning, then she may begin the first IMP intake the next day [Day 2 of the menstrual bleeding]). For a switcher, the first IMP intake will be on the day following the last active pill of the previous hormonal contraceptive. The subject is free to choose an intake time in the morning or evening

that suits her requirements. Breastfeeding women can start the first IMP any day starting six weeks after delivery.

2.4 Randomization

Not applicable. Subjects will be allocated to treatment only if they satisfy all the inclusion criteria and are not precluded from participation by any of the exclusion criteria.

2.5 Treatments

The study product is LF111, which consists of coated tablets containing 4.0 mg DRSP. One package includes 24 active (white) tablets followed by 4 placebo (green) tablets. The dose for each subject is one tablet per day. During each medication cycle, the subjects will take 24 active tablets (each containing 4.0 mg DRSP) followed by 4 placebo tablets.

2.6 Sample Size

At least 920 subjects will be allocated to treatment to have at least 5000 evaluable cycles for the PI calculation in non-breastfeeding women aged ≤ 35 years (at the time of trial enrollment). Additionally, a minimum of 75 subjects aged > 35 years will be allocated to treatment. The calculations are based on empirical values including firstly a rate of 24.8% of subjects using back-up contraception or not having intercourse. Secondly, 45% of subjects are assumed to drop out of the trial. The prime target is to collect at least 5000 evaluable cycles.

2.7 Blinding

Not applicable to this trial.

3. ANALYSIS SETS AND SUBGROUPS

3.1 Analysis Sets

As described in the “CF111303: Site 104: Addendum to Investigation Report Signed 18-August-2016 by [name], SCOPE CRA Manager”, “CF111303: Site 120: Addendum to Serious Breach Reporting Form Signed 23-August-2016 by [name], SCOPE Project Manager” and sponsor letter “RE: Clinical Trial CF111-303: exclude data from analysis for sites 104 and site 120” data from sites 104 and 120 will not be included in any statistical summary or analysis tables. Data from these sites will only be included in the Appendix 4 tables (Tables 15.1.1.1.1, 15.1.2.1.1, 15.1.3.1.1, 15.2.1.2.5, 15.2.1.2.7, 15.2.1.4.3, 15.2.1.4.5, 15.2.1.4.7, 15.2.1.4.9, 15.2.3.1.1 and 15.2.3.1.2), Appendix 5 listings and Appendix 6 figures (Figures 15.1.1.1, 15.1.2.1).

The analyses will be based on the following analysis sets:

Enrolled Set (ES) will consist of all subjects who signed informed consent/assent.

Safety Set (SS) will consist of all subjects who:

- took at least one dose of IMP.

Full Analysis Set (FAS) will consist of all subjects who:

- took at least one dose of IMP;
- were not pregnant at the date of first IMP intake.

Modified Full Analysis Set (MFAS) will consist of all subjects who:

- took at least one dose of IMP;
- were not pregnant at the date of first IMP intake;
- were non-breastfeeding.

Per Protocol Set (PPS) will not be defined since PI will be calculated using three methods therefore protocol violations will be taken into account.

Data of centers 104 and 120 will be excluded for SS and FAS calculations. Data of these centers will also be excluded for MFAS calculations unless it will be specified in the header of the respective tables that data of these centers are included.

3.2 Subgroups

The following subgroups will be defined:

- Weight subgroups, defined as
 - < median weight of the safety set
 - \geq median weight of the safety set
- Body mass index (BMI) subgroups, defined as
 - $BMI < 30 \text{ kg/m}^2$
 - $BMI \geq 30 \text{ kg/m}^2$
 - $25 \text{ kg/m}^2 < BMI < 30 \text{ kg/m}^2$ ¹
- Blood pressure subgroups, defined as
 - Systolic blood pressure (SBP) $< 130 \text{ mmHg}$ and diastolic blood pressure (DBP) $< 85 \text{ mmHg}$
 - Systolic blood pressure (SBP) $\geq 130 \text{ mmHg}$ or diastolic blood pressure (DBP) $\geq 85 \text{ mmHg}$
- Race subgroups, defined as
 - American Indian or Alaska Native
 - Asian
 - Black or African-American

¹ $25 \text{ kg/m}^2 < BMI < 30 \text{ kg/m}^2$ category is in addition to the protocol.

- Native Hawaiian or Other Pacific Islander
- White
- Other
- Ethnicity subgroups, defined as
 - Hispanic or Latino
 - Not Hispanic or Latino

3.3 Data Review

A data review meeting (DRM) will be held after database lock, prior to the final SAP and clinical database closure.

The following aims are defined for the DRM:

- to assign pregnancies to their category and cycle;
- to identify protocol deviations which may have impact on cycles;
- to assign subjects to each of the analysis sets;
- to check that there are no data issues that are outstanding or need resolution;
- to define complete and correct diary entry;
- to solve any outstanding issues in the SAP.

Appropriate trial team, including a physician, will review certain potential protocol deviations and will review relevant information regarding those deviations to determine whether each of them have an impact on a perfect cycle. Protocol deviations will be not categorized into major and minor rather they will be categorized according to their impact to the perfect medication cycle.

Inclusion criterion related deviations will be classified as follows:

Inclusion criteria (At Visit 1 (Screening) and at Visit 1b (Medication Dispensation), subjects must meet ALL of the following criteria)	Impact on the cycle	DRM listing no.

1. Sexually active, postmenarcheal and premenopausal female subjects at risk of pregnancy with no upper age limit.
 
Since Protocol Final Version 4.0: Sexually active, postmenarcheal and premenopausal female subjects at risk of pregnancy including breastfeeding women with no upper age limit.
	Case by case decision	IN01, IN02

2. Female subjects at risk of pregnancy, between the ages of 15 and 17 (inclusive) provided that
 
 • Applicable national, state and local laws allow subjects in this age group to consent to receive contraceptive services, • All applicable laws and regulations regarding the informed consent of the subjects to participate in clinical trials are observed, and • Subjects in this age group will also be encouraged to consistently and correctly use male condoms with every event of sexual intercourse. 
Since Protocol Final Version 4.0: Female subjects at risk of pregnancy, between the ages of 15 and 17 (inclusive) provided that
 
 • Applicable national, state and local laws allow subjects in this age group to consent/assent to receive contraceptive services, and 	All cycles	IN03


 All applicable laws and regulations regarding the informed consent/assent of the subjects to participate in clinical trials are observed. 
3. Regular cycles during the last six months before consent when not using hormonal contraception.
 
Since Protocol Final Version 4.0: Regular cycles during the last six months before consent/assent when not using hormonal contraception.
		

4. Menstruation restarted since last pregnancy (only applicable for women that were pregnant within the last six months), i.e., at least three complete menstrual cycle after delivery.
 
Since Protocol Final Version 4.0: At least three complete menstrual cycles after delivery (only applicable for women who were pregnant within the last six months and for non-breastfeeding women). Breastfeeding women can be included six weeks after delivery irrespective of menstrual cycles post-delivery.
	Case by case decision	IN04

5. At screening, maximum systolic blood pressure (median value of three values) less than or equal to 159 mm Hg and diastolic blood pressure (median value of three values) less than or equal to 99 mm Hg
 
Since Protocol Final Version 4.0: At screening, maximum systolic blood pressure (median value of three values) \leq 159 mmHg and diastolic blood pressure (median value of three values) \leq 99 mmHg.
	No impact	IN06

6. Be able and willing to provide written informed consent/assent, or assent if the subject is adolescent, prior to undergoing any trial related procedure.
 
7. Willing to use trial contraception for thirteen 28-day cycles.
 
8. Be willing to have intercourse each cycle of trial.
 
Since Protocol Final Version 4.0: Be willing to have intercourse each cycle of trial without the need to use back-up contraceptive.
	-	-

9. Be willing to state that, to her best knowledge, her male sexual partner(s):
 
 Has not had a vasectomy or been previously diagnosed as infertile. Has not been previously diagnosed or suspected of human immunodeficiency virus (HIV) unless he has subsequently had a negative HIV test. Has not been known to have engaged in homosexual intercourse in the past five years unless he has had negative HIV test results since then. Has not shared injection drug needles in the past unless he has had a negative HIV test at least six weeks since last use. 
10. Agree not to participate in any other clinical trials during the course of this trial.
	-	-

Exclusion criterion related deviations will be classified as follows:

Exclusion criteria (Subjects are to be excluded from the trial for ANY ONE of the following reasons)	Impact on the cycle	DRM listing no.
1. Pregnant or breastfeeding. Since Protocol Final Version 4.0: Pregnant.	All cycles	DRM01
2. Subject is known to or suspected of not being able to comply with the trial protocol, the use of trial medication or the use of the trial diary.	-	-
3. History of infertility.	All cycles	EX02
4. Abnormal finding on pelvic, breast or ultrasound examination that in the investigator's opinion contraindicates participation in the trial.	Case by case decision	EX03
5. Unexplained amenorrhea.	Case by case decision	EX04
6. Known polycystic ovary syndrome.	Case by case decision	EX05
7. Abnormal Papanicolaou (Pap) smear (ASC-US or more severe finding) at screening. (Pap smear results from within the previous three months prior to consent are acceptable if the report is available to the trial investigator).	Case by case decision	EX06
Since Protocol Final Version 4.0: Women ≥ 21 years of age with a Papanicolaou (pap) smear reading LGSIL or higher at screening (or six months prior to screening date). Human papilloma virus (HPV) testing in subjects with atypical squamous cells of undetermined significance (ASC-US) can be used as an adjunctive test. 
 • Subjects with ASC-US can be included if they are negative for high-risk HPV strains. • Subjects < 21 years of age do not require a pap smear. 		
8. Known contraindication or hypersensitivity to ingredients or excipients of the IMP, including: 
 a. Renal insufficiency b. Hepatic dysfunction c. Adrenal insufficiency d. Current or history of venous thrombophlebitis or thromboembolic disorders (venous thrombembolism; which includes deep vein thrombosis and pulmonary embolism) e. Current or history of cerebral-vascular or coronary-artery disease f. Valvular heart disease with thrombogenic complications g. Diabetes with vascular involvement h. Headaches with focal neurological symptoms i. Major surgery with prolonged immobilization j. Known or suspected carcinoma of the breast k. Known or suspected sex-steroid sensitive malignancies l. Undiagnosed abnormal genital bleeding 	Case by case decision	EX07

m. Cholestatic jaundice of pregnancy or jaundice with prior hormonal contraceptive use		
n. Liver tumor (benign or malignant) or active clinically significant liver disease.		
9. Uncontrolled thyroid disorder (i.e., on stable dose of thyroid replacement for less than two months).	Case by case decision	EX08
10. Uncontrolled concomitant diseases (i.e., not on a stable treatment dose for at least two months).	Case by case decision	EX09
11. Evidence or history of alcohol, medication or drug abuse (within the last 12 months).	Case by case decision	EX10
Since Protocol Final Version 4.0: Evidence or history of alcohol, medication or drug abuse (within the last 12 months prior to consent/assent).		
12. Known inherited or acquired predisposition to VTE or ATE (e.g. factor V _{Leiden} , Prothrombin mutation, Antiphospholipid-antibodies) or bruising within the last 12 months prior to consent.	No impact	EX11, EX12
Since Protocol Final Version 4.0: Known inherited or acquired predisposition to venous thromboembolism or arterial thromboembolism (e.g., factor V _{Leiden} , Prothrombin mutation, Antiphospholipid-antibodies) or bruising within the last 12 months prior to consent/assent.		
13. Known or suspected HIV and/or hepatitis infection at screening.	All cycles	EX13
14. Received a dose of depot medroxyprogesterone acetate (DMPA or Depo-Provera) during the 10 months prior to consent, or received any combined injectable contraceptive (e.g., Cyclofem) during the six months prior to consent, or no spontaneous menses since last injection.	Case by case decision	EX14
Since Protocol Final Version 4.0: Received a dose of depot medroxyprogesterone acetate (DMPA or Depo-Provera®) during the 10 months prior to consent/assent, or received any combined injectable contraceptive (e.g., Cyclofem®) during the six months prior to consent/assent, or no spontaneous menses since last injection.		
15. Long-term treatment (longer than seven consecutive days) within a month prior to V1b of any medication that might interfere with the efficacy of hormonal contraceptives. Prohibited medication include: a. Anticonvulsants (e.g. Phenytoin, carbamazepine, oxcarbazepine, topiramate, felbamate, primidone) b. Barbiturates c. Rifampin d. Atorvastatin e. Bosentan f. Griseofulvin g. Phenylbutazon h. St. John's wort (hypericum perforatum)	Case by case decision	EX15
Since Protocol Final Version 4.0:		

Long-term treatment (longer than seven consecutive days within a month prior to V1b) of any medication that might interfere with the efficacy of hormonal contraceptives. Prohibited medication include: 
 Anticonvulsants (e.g. phenytoin, carbamazepine, oxcarbazepine, topiramate, felbamate, primidone) Barbiturates Rifampin Bosentan Griseofulvin St. John's wort (hypericum perforatum) 		
16. Administration of human chorionic gonadotropin (hCG) or intake of co-medication containing hCG within a month prior to V1b.	Case by case decision	EX16
17. Progestin-releasing IUD or contraceptive implant received or in place within the last two months prior to consent.	Case by case decision	EX17
Since Protocol Final Version 4.0:		
Progestin-releasing intra-uterine device (IUD) or contraceptive implant received or in place within the last two months prior to consent/assent.		
18. Planned regular concomitant use of barrier contraceptive methods, spermicides, IUDs or other contraceptive measures (excepting occasional use for safety reasons, e. g. reduce risk of infection).	-	-
Since Protocol Final Version 4.0:		
Planned regular concomitant use of barrier contraceptive methods, spermicides, IUDs or other contraceptive measures (excepting occasional use for safety reasons, e. g. reduce risk of infection).		
19. Evidence or history of clinically significant psychiatric illness or suicide risk.	No impact	EX18
20. Participation in another trial of an investigational drug or device parallel to the current trial, or less than 90 days before consent, or previous participation in the current trial and dispensed trial medication.	-	-
Since Protocol Final Version 4.0:		
Participation in another trial of an investigational drug or device parallel to the current trial or less than 90 days before consent/assent, or previous participation in the current trial and dispensed trial medication.		
21. Subject is a member of the investigator's or Sponsor's staff or a relative or family member thereof.	-	-
22. Any condition that, in the opinion of the investigator, may jeopardize protocol compliance or the scientific integrity of the trial.	-	-

Listings related to Inclusion/Exclusion criterions:

Number	Name
Listing IN01	Subjects with Missing Age at Menarche
Listing IN02	Sexually Non-Active Subjects.
Listing IN03	Subjects with Missing Consent/Assent Date
Listing IN04	Subjects with Non-Regular Menstrual Bleeding During the Last 6 Cycles Before Visit 1a

Listing IN05	Non-Breastfeeding Subjects Who Had Delivery Within the Last Six Months or Breastfeeding Subjects Who Had Delivery Within Less than Six Weeks Before Visit 1a
Listing IN06	Subjects with Maximum SBP \geq 159 mmHg or DBP \geq 99 mmHg at Visit 1a
Listing EX02	Subjects with History of Infertility
Listing EX03	Subjects with Abnormal Finding on Pelvic, Breast or Ultrasound Examination
Listing EX04	Subjects with Unexplained Amenorrhea
Listing EX05	Subjects with Known Polycystic Ovary Syndrome
Listing EX06	Subjects \geq 21 Years of Age with Abnormal Papanicolaou Smear Reading or Positive Human Papilloma Virus Test
Listing EX07	Subjects with Known Contraindication or Hypersensitivity to Ingredients or Excipients of the IMP
Listing EX08	Subjects with Uncontrolled Thyroid Disorder
Listing EX09	Subjects with Uncontrolled Concomitant Diseases
Listing EX10	Excessive Drinkers
Listing EX11	Subjects with Known Inherited Predisposition to Thromboembolic Illness
Listing EX12	Subjects with Acquired Predisposition to Thromboembolic Illness or Bruising Within the Last 12 Months Prior to Visit 1a
Listing EX13	Subjects with Known or Suspected HIV and/or Hepatitis Infection at Visit 1a
Listing EX14	Subjects Who Received a Dose of Depot Medroxyprogesterone Acetate During the 10 Months Prior to Visit 1a, or Received Any Combined Injectable Contraceptive During the 6 Months Prior to Visit 1a
Listing EX15	Subjects with Long-Term Treatment of Any Medication That Might Interfere with the Efficacy of Hormonal Contraceptives Prior to Visit 1b
Listing EX16	Subjects Who Received Human Chorionic Gonadotropin or Co-Medication Containing Human Chorionic Gonadotropin Within a Month Prior to V1b
Listing EX17	Subjects with Progestin-Releasing Intra-Uterine Device or Contraceptive Implant Received or in Place within the Last 2 Months Prior to Visit 1a
Listing EX18	Subjects with history of clinically significant psychiatric illness or suicide risk

Additional trial conduct criteria deviations will be classified as follows:

Number	Name
Listing DRM01	Subjects Who Became Pregnant During the Study
Listing DRM02	Cycles when Vomiting or Diarrhea is Documented
Listing DRM03	Cycles with Administration of Prohibited Concomitant Therapy
Listing DRM04	Subjects Who did not Meet Inclusion/Exclusion Criterions
Listing DRM05	Listing and Chart with Treatment Cycles
Listing DRM06	IMP Gaps of More Than 48 Hours
Listing DRM07	Adverse Events of Special Interest
Listing DRM08	Non-Complete or Non-Correct Treatment Diary Records
Listing DRM09	Specification of Subject Withdrawn During Treatment
Listing DRM10	Specification of Subject Withdrawn During Screening
Listing DRM11	Protocol Deviation from eCRF
Listing DRM12	Scenarios for first IMP intake preceding V1b
Listing DRM13	Subjects with Partial Date of Last IMP Intake in eCRF
Listing DRM14	Treatment Compliance According to Drug Accountability
Listing DRM15	Subjects for Whom IMP Was Dispensed but Have No eDiary Records
Listing DRM16	Subjects Who Have Cyst Larger Than 30 mm

All decisions made during DRM will be documented in the DRM report.

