2. PROTOCOL SYNOPSIS

Name of sponsor/company: Laboratorios León Farma S.A.	
Name of active ingredient: Drospirenone (DRSP)	
Title of trial: A Pivotal, Multicenter, Non-Comparative Trial on the Contraceptive Efficacy, Safety, Tolerability and Pharmacokinetics of LF111 (Drospirenone 4.0 mg) During 13 Cycles	
Trial number: CF111/303	
IND number: 111347	
Coordinating investigator: [name], MD	
Trial center(s): Approximately 40 centers located in the United States of America	
Planned duration of the trial: First subject first visit: October 2014 Last subject last visit: July 2017	Phase of development: III
Subject recruitment: 20 months	
Objectives: Primary: To demonstrate the contraceptive efficacy of LF111 Secondary: To demonstrate the safety and tolerability of LF111 and assess the pharmacokinetics of LF111	

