5.4.2 Efficacy Analysis	Definitions of Method failure pregnancy, Evaluable cycle and Perfect cycle was updated.
5.6.1 Adverse Events	Safety tables will not consist of data from 104 and 120 sites.

Version Draft 0.5 (10-NOV-2017):

Section	Updates
2.2.4 Tolerability Endpoints	Period 2-13 was added.
3.3 Data Review	DRM listings were updated.
4.6 Trial Periods	Definitions of Date of the first/last IMP intake and baseline value were updated.
5.2.3 Medical History	Definition of current medical history condition was updated.

Version Draft 0.6 (22-NOV-2017):

Section	Updates
All	New tables were added: 15.1.4.1.2, 15.2.1.2.4, 15.2.1.2.5, 15.2.1.2.6, 15.2.1.2.7, 15.2.1.4.3, 15.2.1.4.4, 15.2.1.4.5, 15.2.1.4.6, 15.2.1.4.7, 15.2.1.4.8, 15.2.1.4.9, 15.3.1.8.1, 15.3.1.8.2, 15.3.1.8.3, 15.3.1.8.4, 15.3.1.8.5, 15.3.1.8.6, 15.3.6.1.2, 15.3.7.1.2, 15.3.8.1.2, 15.3.9.1.2, 15.4.4.1.1, 15.4.4.2.1, 15.4.4.3.1, 15.4.5.1.1, 15.4.6.1.1, 15.4.6.2.1, 15.4.6.3.1.
All	Analysis set for Table 15.1.3.1.1 and Listing 16.2.1.2, 16.2.1.14, 16.2.1.15 was changed.
3.1 Analysis Sets	Definition of allocated to treatment set was deleted. Definition of Full analysis and modified full analysis sets were changed.
3.2 Subgroups	Median weight subgroup was updated.
4.6 Trial Periods	Definitions of Date of the first/last IMP intake and baseline value were updated
5.1.1 Disposition and Withdrawals	New subcategories ("IMP related", "non-IMP related" and "Uncategorized") were included.

5.5 Efficacy Analysis	Analysis of withdrawn reasons were expanded. Suspected, subject confirmed not pregnant definition was added. Non-confirmed pregnancy definition and perfect cycle definitions were updated. Tables titles were updated.
-----------------------	--

Version Draft 0.7 (08-DEC-2017):

Section	Updates
All	New tables were added: 15.2.1.2.8_add, 15.2.1.2.9_add, 15.2.1.2.10_add, 15.2.1.2.11_add, 15.2.1.4.10_add, 15.2.1.4.11_add, 15.2.1.4.12_add, 15.2.1.4.13_add, 15.4.7.1.1_add, 15.4.7.2.1_add, 15.4.7.3.1_add. New figures were added: 15.2.1.1_add, 15.2.1.2_add, 15.2.1.3_add, 15.2.1.4_add, 15.2.2.1_add, 15.2.2.2_add, 15.2.2.3_add, 15.2.2.4_add, 15.4.9.1_add, 15.4.9.2_add, 15.4.9.3_add, 15.4.10.1_add, 15.4.10.2_add, 15.4.11.1_add, 15.4.11.2_add
INTRODUCTION	Explanatory legend was included.
2.2 Trial Endpoints	Additional endpoints were added.
5.2.1 Demographics	Age subgroups were corrected.
5.5 Efficacy Analysis	Exposure and perfect cycle definition was updated.

Sponsor: Laboratorios León Farma S.A.

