- **Probable:** A clinical event, including laboratory test abnormality, with a reasonable time sequence to administration of the drug, unlikely to be attributed to concurrent disease or other drugs or chemicals, and which follows a clinically reasonable response on withdrawal (dechallenge). Rechallenge information is not required to fulfil this definition.
- **Definite:** A clinical event, including laboratory test abnormality, occurring in a plausible time relationship to drug administration, and which cannot be explained by concurrent disease or other drugs or chemicals. The response to withdrawal of the drug (dechallenge) should be clinically

plausible. The event must be definitive pharmacologically or phenomenologically, using a satisfactory rechallenge procedure if necessary.

Related AEs include the categories “possible”, “probable” and “definite”.

Unrelated AEs include the categories “unrelated” and “unlikely”.

The relationship of an AE to the IMP will be defined as “Unknown” if relationship grade assessment is missing.

Treatment Emergent Adverse Events

An AE that emerges during treatment having been absent prior to treatment or worsens relative to the pre-treatment state is defined as treatment emergent adverse event (TEAE). All AEs with onset or worsening after first intake of IMP until 10 days after last intake of IMP are defined as treatment emergent.

Where only partial dates are present, the month and/or year may be sufficient alone for assignment of treatment emergent AEs but in cases where this is not possible these AEs will be considered as treatment emergent.

Serious Adverse Events

An AE or suspected adverse reaction is considered “serious” if, in the view of either the investigator or sponsor, it results in any of the following outcomes:

- Death
- A life-threatening
- Inpatient hospitalization or prolongation of existing hospitalization
- A persistent or significant incapacity or substantial disruption of the ability to conduct normal life functions
- Congenital anomaly/birth defect

Adverse Events of Special Interest

Adverse events of special interest will be defined as hyperkalemia and venous thromboembolism events. Hyperkalemia will be identified as AEs with preferred terms “Hyperkalaemia” and “Blood potassium increased”. Venous thromboembolism will be identified as embolic and thrombotic venous events and assignments will be handled by Medical Monitors after database closure.

Adverse events leading to trial termination

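### Choices that decide which pregnancies enter the Pearl Index may still be made after database lock, with the pregnancies known and the SAP not yet final

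*SAP*

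**What the plan says.** SAP 3.3 fixes the order of events: "A data review meeting (DRM) will be held after database lock, prior to the final SAP and clinical database closure". The aims listed for the data review meeting (DRM) include "to assign pregnancies to their category and cycle", "to assign subjects to each of the analysis sets" and "to solve any outstanding issues in the SAP". The last has no limit on scope.

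The same section has the team judge whether deviations affect a perfect cycle. Fourteen eligibility criteria in its tables are left to case-by-case decision. Listing DRM01 (women who became pregnant) belongs to the same package as the deviation listings. Decisions are to be recorded in a DRM report.

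SAP 5.5.1 bases the primary PI on evaluable cycles of non-breastfeeding women aged 35 or younger in the MFAS, and Table 15.2.1.1.1 counts confirmed on-drug pregnancies only. SAP 2.2.1 excludes conceptions dated more than seven days after the last tablet. It ranks the dating methods, with the investigator's estimate last.

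The SAP version history for the draft of 8 December 2017 records: "Exposure and perfect cycle definition was updated". The draft of 22 November 2017 changed the full and modified full analysis set definitions. The protocol synopsis plans "Last subject last visit: July 2017".

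**The concern.** With no control arm, nothing offsets a choice made with the outcome in view: it moves the absolute estimate directly. Pregnancies are few, so each one carries weight. If the rules are open when the team meets, the question of which rule to adopt cannot be separated from the question of which women it would count.

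The documents available describe neither pregnancy-masked review nor independent adjudication. At stake is the credibility of the primary PI, and more so of the method-failure PI, where more is left to judgement.

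**Working it through.** **Step 1. Which decisions reach which estimate.**

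*Primary PI, four routes:*
- Category. Only confirmed pregnancies count, and the SAP 5.5 definitions do not settle every case. A woman with one confirmatory test negative and the other missing fits both suspected categories, since each is worded with and/or. All three categories start from a positive home test, so a pregnancy found only at a visit fits none of them.
- Dating. The seven-day rule makes a conception on-drug or off-drug. When ultrasound is lacking, the date rests on weaker methods.
- Set membership. The MFAS excludes women pregnant at first intake, so dating matters at the start of treatment too.
- Open SAP issues. Evaluable cycles are a subset of exposure cycles, so a change to the exposure definition can carry through to the primary denominator.

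*Method-failure PI and life table only:*
- The case-by-case eligibility rulings act on perfect cycles. The exposure and evaluable definitions in SAP 5.5 contain no deviation criterion.
- Drug levels may be used to judge non-compliance where thought necessary, with no threshold given.
- The footnote to the SAP 5.5 definitions ties a cycle's perfect status to the status of its pregnancy, in both directions.

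**Step 2. The plan's own figure.** Inputs from SAP 2.6 and the synopsis: 920 women, 13 cycles, 24.8% with back-up use or no intercourse, 45% dropout.

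920 × 13 × (1 − 0.248) × (1 − 0.45) = 4947 cycles, 1.1% below 5000. Conversely, 5000 / (13 × 0.752 × 0.55) = 930 women. The stated 920 is reproduced closely, and 5000 is used below.

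**Step 3. Leverage on the primary PI.** PI = 1300 × k / cycles, so one pregnancy is 1300 / 5000 = 0.26. The exact Poisson 95% limits are 0.26 × 0.5 χ²(0.025; 2k) and 0.26 × 0.5 χ²(0.975; 2k + 2). The upper limit as it reads in SAP 5.5 (0.025 quantile, 2k + 1 degrees of freedom) would fall below the PI itself, 1.34 against 2.60 at k = 10. It is not used here; it is a separate matter and may be an artefact of text extraction.

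The documents give no expected number of pregnancies, so k is an assumption and a range is shown.

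| Pregnancies (assumed) | PI (95% CI) | After reclassifying 2 | Relative fall |
|---|---|---|---|
| 10 | 2.60 (1.25–4.78) | 2.08 (0.90–4.10) | 2/10 = 20% |
| 15 | 3.90 (2.18–6.43) | 3.38 (1.80–5.78) | 2/15 = 13% |
| 20 | 5.20 (3.18–8.03) | 4.68 (2.77–7.40) | 2/20 = 10% |

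Reclassifying a single pregnancy lowers the upper limit from 4.78 to 4.44 at k = 10 and from 6.43 to 6.11 at k = 15.

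**Step 4. Leverage on the method-failure PI.** Assume 4000 perfect cycles and 10 method-failure pregnancies: 1300 × 10 / 4000 = 3.25 (1.56–5.98). Ruling two pregnancy cycles not perfect gives 1300 × 8 / 3998 = 2.60 (1.12–5.13). Removing a few cycles without a pregnancy hardly changes the result, so the rulings that matter are those on cycles with a pregnancy.

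**The case against.** The plan already has safeguards. Pregnancy categories are written down and based on tests. First-trimester ultrasound dating cannot be revised by later scans. A pregnancy brings its cycle into the evaluable set even with back-up use or no reported intercourse, which works against a favourable PI. The tablet-gap and missed-tablet limits for perfect cycles are numeric. Tables 15.2.1.4.4 and 15.2.1.4.5 add suspected, non-confirmed pregnancies in the primary population, without and with sites 104 and 120.

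These points stand and narrow the exposure. They do not close it. The added tables reveal a move from confirmed to suspected, but they cannot recover a pregnancy ruled not to exist, dated off-drug, or lost with a woman left out of the MFAS. No planned table varies the perfect-cycle rulings. The DRM report records decisions without preventing outcome-aware ones.

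A reader might infer more than the documents support:
- *That the rules were changed after lock.* The draft log is consistent with late changes. But July 2017 is a planned date, no lock or DRM date is given, and the draft of 10 November 2017 was still updating the DRM listings. Lock and closure are also not defined, so a soft lock is possible.
- *That every DRM decision bears on every efficacy estimate.* The case-by-case rulings do not reach the primary or overall PI.
- *That the aim "to define complete and correct diary entry" affects the PI.* SAP 4.8 defines such entries by reference date and bleeding fields, and they serve the bleeding analyses.
- *That late assignment of thromboembolic events belongs here.* It is a safety matter (SAP 5.6.1) and does not enter the PI.

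It is also fair to object that in an open-label trial pregnancies are seen as they occur, so signing the SAP before lock cannot make the rules fully outcome-blind.

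**Conclusion.** The point holds as one of opportunity, arising from an order of events that the SAP states outright. The primary PI is exposed through pregnancy category, on-drug dating, MFAS assignment and the open-ended item on SAP issues. The method-failure PI and life table are exposed further, through the case-by-case rulings and the discretionary use of drug levels.

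The size is 0.26 PI per pregnancy at the target of 5000 evaluable cycles. For two reclassified pregnancies this is 0.52, or 10% to 20% of the PI over the assumed 20 to 10 pregnancies. Both the total and the number reclassified are assumptions. The documents at hand state no PI limit for success, so whether such a shift would alter a conclusion cannot be judged. Nothing in them shows that any estimate was shaped. This is an inexpensive improvement worth making, and not evidence that the result is biased.

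**What to change.** In SAP 3.3, require the SAP to be signed before database lock and before the DRM, with the rules fixed for pregnancy category, on-drug dating, analysis sets, and exposure, evaluable and perfect cycles. Remove the open-ended aim of settling SAP issues at the meeting.

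Run the DRM in two stages:
1. Classify deviations for their effect on perfect cycles using listings stripped of pregnancy status. This includes pregnancy as a withdrawal reason, which would otherwise show in DRM09. Record the decisions.
2. Open DRM01 and apply the fixed pregnancy rules.

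Label any later rule change post hoc and report the affected PI under both versions. If lock has already passed, this last step can still be taken.

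The cost is a reordering of existing steps, some listing work and less freedom to resolve late data issues. Sample size and the 5000-cycle target do not change. Because the trial is open-label, the change reduces outcome-aware discretion but does not eliminate it.
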